6.1.3. VARIABLES GENERATED FROM SF-36v2

The scoring for SF-36 v2 instrument will be done according to the procedures described by the developer and license owner in the instruction manual. Scores for the scales (HT, GH, PF, RP, BP, MH, SF, RE, VT) as well as the summary scores (PCS, MCS) will be derived. For the psychometric analysis only the baseline scores will be used.

6.1.4. VARIABLES GENERATED FROM EQ-5D-5L

No derivation is required for the EQ-5D-5L. The scores for the 5 domains (Mobility, Self-care, Usual Activities, Pain/discomfort and Anxiety/depression) and EQ-5D VAS will be as reported. Missing data for individual items will not be imputed. For the psychometric analysis only the baseline scores will be used.

6.1.5. VARIABLES GENERATED FROM PGIS AND PGIC

The PGIS and PGIC are single-item questionnaires. Therefore, they do not require any manipulation to derive scores.

To be noted that PGIS is collected on the last day of CARES assessment period. To be in line with the visit label used for CARES, we will label the PGIS assessment from Week 12 as Week 13 (Visit 7). For the psychometric analysis, the baseline scores (PGIS only), Week 13 and Week 24 will be used.

6.2. CLINICAL OUTCOME VARIABLES

Demographic and clinical data will be used to characterize the sample, as follows:

- Age (years)
- Sex
- Race

Document : /Users/[REDACTED]/Dropbox (Corvidia Tx)/Corvidia Tx Team Folder/Assets/COR-001/Clinical/RESCUE (COR-001-02)/Manuals & Plans/PRO
PAP/Corvidia_RESCUE_PAP_FinalV2.0_24APR2020.docx

Author: [REDACTED] Version No: V2.0

Version Date: 24APR2020

Template No.: [REDACTED] Reference: [REDACTED]

Effective Date: 01Dec2018

Copyright © 2018 [REDACTED] All rights reserved. The contents of this document are confidential and proprietary to [REDACTED] and its subsidiaries. Unauthorized use, disclosure or reproduction is strictly prohibited.

- Baseline Hemoglobin (≥ 11 or < 11 g/dL)
- CKD Stage (Stage 3, Stage 4, or Stage 5)

The clinical variable that will be used in the psychometric evaluation is the total plasma level for the hs-CRP Protein.

6.3. GENERAL VARIABLES AND DEFINITIONS

6.3.1. BASELINE

The baseline for CARES will be defined as the weekly-average of the daily measurements over the 7-day period immediately preceding randomization day (i.e., study days -7 through -1), e.g., the second week of the screening period.

For all other PRO instruments, except PGIC, the baseline is defined as the measurements carried out at clinic prior to first dose of the study drug, scheduled for the 1st day of the Treatment Period. There will be no baseline assessment for PGIC.

6.3.2. DERIVED TIMEPOINTS

No other timepoints are derived.

7. STATISTICAL METHODOLOGY

7.1. GENERAL CONSIDERATIONS

Summary statistics for continuous data will include the number of observations (N), mean, standard deviation (SD), median, first and third quartiles, minimum (min), and maximum (max). Categorical data will be described by the number (n) and percentage (%) of patients in each category. Missing and invalid observations will be tabulated as separate categories. The calculation of proportions will not include the missing/invalid category, unless specified otherwise.

Statistical comparisons will be made using two-sided tests at the $\alpha = 0.05$ significance level unless stated otherwise. Due to the exploratory nature of these analyses, no adjustments for multiplicity will be performed. For point estimates, 95% confidence intervals will be used.

The psychometric analysis will be performed on the pooled treatment arms.

Document : /Users/████████/Dropbox (Corvidia Tx)/Corvidia Tx Team Folder/Assets/COR-001/Clinical/RESCUE (COR-001-02)/Manuals & Plans/PRO
PAP/Corvidia_RESCUE_PAP_FinalV2.0_24APR2020.docx

Author: ██████████ Version No: V2.0

Version Date: 24APR2020

Template No.: ██████████ Reference: ██████████

Effective Date: 01Dec2018

Copyright © 2018 ██████████ All rights reserved. The contents of this document are confidential and proprietary to ██████████ and its subsidiaries. Unauthorized use, disclosure or reproduction is strictly prohibited.

7.2. STUDY SUBJECTS

7.2.1. PRO COMPLETION

The completion rate for CARES will be defined as the total number of actual completed diary entries divided by the expected number of diary entries in a given time period (total number of days X number of patients expected to complete the instrument). Specifically, completion rate will be evaluated for the baseline period (Day -7 to Day -1), in the weeks prior to each clinic visit for administration of dosage (Day 22 to 28 [Week 5] and 78 to 84 [Week 13]), and Day 155 to 168 [Week 24].

For the *PROMIS* Fatigue, *PROMIS* Sexual Interest, PGIC and PGIS, completion rates will be calculated as the total number of actual completed clinic visit entries divided by the expected number of patients taking part in the scheduled clinic visit.

7.2.2. DEMOGRAPHICS AND BASELINE CHARACTERISTICS

The demographic and patient baseline characteristics are analyzed in the clinical SAP and will not be repeated herein.

7.3. MEASUREMENT PROPERTIES ANALYSES

The analyses described below follow best practice guidelines for the psychometric analysis of PRO measures according to the FDA guidance [FDA 2009, FDA 2019].

7.3.1. DESCRIPTIVE ANALYSES

Descriptive statistics for CARES, *PROMIS* Fatigue, *PROMIS* sexual function and satisfaction, PGIC, and PGIS will be assessed by evaluating the following at baseline, Visit 4, and Visit 7:

- Counts and percentages for each response option per item, including a stacked column chart of the distribution of responses
- Summary statistics for each item of CARES, *PROMIS* Fatigue, *PROMIS* sexual function and satisfaction
- Summary statistics for each scale/domain and total score of CARES and *PROMIS* Fatigue

Item descriptive analyses will be examined for CARES and *PROMIS* Fatigue for item removal, combined with qualitative evaluation. Specifically, items with floor or ceiling effect (e.g., items

Document : /Users/[REDACTED]/Dropbox (Corvidia Tx)/Corvidia Tx Team Folder/Assets/COR-001/Clinical/RESCUE (COR-001-02)/Manuals & Plans/PRO
PAP/Corvidia_RESCUE_PAP_FinalV2.0_24APR2020.docx

Author: [REDACTED] Version No: V2.0
Version Date: 24APR2020

Template No.: [REDACTED] Reference: [REDACTED]

Effective Date: 01Dec2018

Copyright © 2018 [REDACTED] All rights reserved. The contents of this document are confidential and proprietary to [REDACTED] and its subsidiaries. Unauthorized use, disclosure or reproduction is strictly prohibited.

that are disproportionately rated at either extreme of their rating scales by patients at baseline and/or after treatment) will be considered as candidates for item reduction.

7.3.2. ITEM-TO-ITEM CORRELATIONS FOR CARES AND PROMIS FATIGUE ITEMS

The purpose of item-to-item correlation analyses is to evaluate inter-relationships among items to determine the extent and degree of correspondence and discordance between items, and whether those patterns are consistent with hypothesized expectations based on the item content.

Spearman rank correlation coefficient will be calculated using baseline data to examine the inter-relationships among items for CARES (Items 1 to 19) and among *PROMIS Fatigue* Items (Fatigue 13a Items 1 to 13, Fatigue Bank Items FATEXP36, FATEXP43 and FATEXP52).

Correlations greater than 0.4 may provide support for combining items into a multi-item scale. Items with coefficients greater than 0.9 and/or less than 0.1 may be considered for item removal.

7.3.2.1. CARES

The CARES instrument is organized thematically in different sets of symptoms. Items 1 to 7 describe a set of physiological symptoms (Short Breath, Swelling, Fatigue, Weakness, Light-headedness, Decreased Appetite, Nausea). Items 8 to 10 cover psychological issues (Depression, Concentration, Forgetfulness). Item 11 to 13 describe pain (Nerve, Bones/Joints, Muscle Cramps).

The remainder of the items cover a variety of sensorial symptoms that can be loosely described as a sensation of uncomfortableness, mostly associated with the skin and terminal nervous system (Hand numbness/tingling, Uncomfortable legs, Itching, Dry skin, Dry mouth, Cold). Correlations may vary accordingly in a non-predictable manner.

7.3.2.2. PROMIS Fatigue

The combined set of fatigue items is quite homogeneous with regards to the topics investigated. Specifically, the fatigue Bank additional items may be reasonably perceived as 'general' feelings of fatigue/exhaustion and therefore be strongly correlated with the short form 13a Items. It is expected that these items will show strong correlations (above 0.50) across the items.

7.3.3. EXPLORATORY FACTOR ANALYSIS

An exploratory factor analysis (EFA) will be carried out for the items of CARES and *PROMIS Fatigue* to test the measurement model. EFA is a model of the measurement of a latent variable. This latent variable cannot be directly measured with a single variable. Instead, it is seen through the relationships it causes in a set of variables. The relationships between the

Document : /Users/████████/Dropbox (Corvidia Tx)/Corvidia Tx Team Folder/Assets/COR-001/Clinical/RESCUE (COR-001-02)/Manuals & Plans/PRO
PAP/Corvidia_RESCUE_PAP_FinalV2.0_24APR2020.docx

Author: ██████████ Version No: V2.0

Version Date: 24APR2020

Template No.: ██████████ Reference: ██████████

Effective Date: 01Dec2018

Copyright © 2018 ██████████ All rights reserved. The contents of this document are confidential and proprietary to ██████████ and its subsidiaries. Unauthorized use, disclosure or reproduction is strictly prohibited.

factor(s) and each variable are weighted, and factor analysis calculates the optimal weights.

The Kaiser-Meyer-Olkin measure of sampling adequacy will be used to evaluate the strength of the linear association among the items in the correlation matrix. The KMO measure can range between 0 and 1. The standard threshold value for sample adequacy is above 0.6, with 0.8 and above being ideal [Pett et al. 2003].

Both the maximum likelihood (ML) and the unweighted least squares (ULS) extraction method will be used in this study. ML is the most frequently used factor extraction methods. However, it does require the assumption of multivariate normal distribution of the variables. If the assumption of multivariate normality is severely violated (e.g., skewness < -1 or > 1), Fabrigar et al. 1999 and Nunnally and Bernstein 1994 recommend using ULS.

The symptoms investigated in the two PROs under investigation are expected to be associated with each other. We expect the underlying domains to be correlated. Accordingly, the EFA will be executed using a PROMAX rotation. The number of factors will be determined using established methods (Eigenvalues assessments, scree-plots).

The PROC FACTOR procedure in SAS will be used to perform the EFA.

A total summary scale or set of scales will be proposed in light of the factor loadings and clinical and conceptual considerations. The score(s) developed as psychometrically sound will be used to evaluate efficacy.

Data distributions and correlations with other PROs will then be carried out for the proposed CARES and PROMIS Fatigue scales and/or subscales as described in sections 7.3.5 and 7.3.6.

7.3.4. ITEM-TOTAL CORRELATIONS FOR CARES AND PROMIS FATIGUE

Correlations between items and scales derived using the preliminary algorithm and possible alternative structures selected from the factor analysis will be assessed using baseline data. The multitrait-multimethod approach will be applied to assess the association of items with their hypothesized scales (item removed) and the association of items with other scales. Spearman rank correlations will be estimated for this analysis. Items are expected to have a correlation coefficient >0.4 with their hypothesized scales (convergent validity) and to have a higher correlation with their hypothesized scale than with any other scale (divergent validity).

Item-total correlations will be considered adequate if the Spearman rank correlation coefficient values are at least 0.40. Any low item-total correlations will be flagged, and item removal will be considered, as it may indicate inadequate scale validity. Any large correlation coefficient (e.g., ≥ 0.90) might suggest redundancy, marking the item as a candidate for elimination or modification.

Document : /Users/[REDACTED]/Dropbox (Corvidia Tx)/Corvidia Tx Team Folder/Assets/COR-001/Clinical/RESCUE (COR-001-02)/Manuals & Plans/PRO
PAP/Corvidia_RESCUE_PAP_FinalV2.0_24APR2020.docx

Author: [REDACTED] Version No: V2.0
Version Date: 24APR2020

Template No.: [REDACTED] Reference: [REDACTED]

Effective Date: 01Dec2018

Copyright © 2018 [REDACTED] All rights reserved. The contents of this document are confidential and proprietary to [REDACTED] and its subsidiaries. Unauthorized use, disclosure or reproduction is strictly prohibited.

7.3.5. RELIABILITY

7.3.5.1. Test-Retest Reliability

Test-retest reliability (i.e., the stability of an instrument over time) will be assessed using intra-class correlation coefficients (ICCs) between two time points ("test" and "retest"), employing form 2.1 as described by [Shrout and Fleiss 1979](#). For CARES, two sets of data will be examined: for the 7 days prior to treatment on Day 1 for all patients and Visit 4 period for patients considered to be in a stable condition, as described below. For *PROMIS Fatigue* only the second set of data will be used, e.g., using patients considered to be in a stable condition.

Systematically selected days

The last 7 days before Day 1 will be considered to define the test and retest time points for CARES collected via eDiary. Test and retest periods will be defined using two consecutive days from the baseline period (Day -6 to Day 1). The following pairs of consecutive days will be evaluated: Days -6 and -5; -5 and -4; -4 and -3; -3 and -2; -2 and -1; -1 and 1.. This analysis will be performed for CARES only.

Stable condition defined using PGIC

Only those subjects reporting "no change" from baseline on the PGIC at Visit 4 will be included. Period 1 (i.e., test) will be defined as baseline and Period 2 (i.e., retest) will be defined as Visit 4.

Stable condition defined using PGIS

Only those patients reporting no change on the PGIS, i.e., those that report the same severity level from baseline to Visit 4, will be included for test-retest investigation. Period 1 (i.e., test) will be defined as baseline and period 2 (i.e., retest) will be defined as Visit 4.

Test-retest reliability will be tested for each multi-item scale/domain as defined by the review of EFA results and total scores. ICC values of 0.40–0.75 will be considered to represent fair to good reliability and values >0.75 represent excellent reliability.

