2.4.2. ASSESSMENT SCHEDULE FOR PRO INSTRUMENTS

Patient-reported outcomes will be assessed through a personal device supplied by Corvidia:

- At home daily on subject personal device: CARES;
- At the clinic prior to dosing on subject personal device: *PROMIS Fatigue*, *PROMIS Interest in Sexual Activity* item, SF-36v2, EQ-5D-5L, PGIC, PGIS .

CARES data will be collected at home on subject's personal device or one provided by Corvidia; the questionnaire will be answered daily for 7 days prior to dose (Screening Day -7 to Day -1 prior to Dose 1 (Visit 1), Dose 2 (Visit 4), Dose 4 (Visit 7), and the last 2 weeks after Dose 6 (Visit 9).

The SF-36v2 and PROMIS Fatigue items are to be collected on subjects' devices at the clinic prior to each dosing, e.g., Visit 1, Visit 4, Visit 7, and at Visit 10 and Visit 11, except for PROMIS Sex Item (Only Visit 11) or the early termination visit (whichever occurs first).

The EQ-5D-5L will be collected on patients' device at the clinic prior to treatment administration at Visit 1, Visit 4, Visit 7 and Visit 11.

The PGIC will be collected on patients' device at the clinic prior to treatment administration at Visit 4, Visit 7, and Visit 11. The PGIS will be collected at home on subjects' devices on the last day of CARES assessment period.

The schedule of assessment for all PRO instruments collected in different periods of the study are shown in Table 1.

Document : /Users/[REDACTED]/Dropbox (Corvidia Tx)/Corvidia Tx Team Folder/Assets/COR-001/Clinical/RESCUE (COR-001-02)/Manuals & Plans/PRO PAP/Corvidia_RESCUE_PAP_FinalV2.0_24APR2020.docx

Author: [REDACTED] Version No: V2.0

Version Date: 24APR2020

Template No.: [REDACTED] Reference: [REDACTED]

Effective Date: 01Dec2018

Copyright © 2018 [REDACTED] All rights reserved. The contents of this document are confidential and proprietary to [REDACTED] and its subsidiaries. Unauthorized use, disclosure or reproduction is strictly prohibited.

Table 1: Schedule of assessment for PRO instruments collected in the RESCUE study- Randomization, treatment period, and follow-up

Study Period	Screening	Treatment											Safety F/Up ^b		
Visit Number	-2 -1	1	2	3	4	5	6	N/A	7	8	9	10	11/ET ^c	12	13/ET
Visit Week	-2 -1	1	2	4	5	7	9	12	13	17	21	23	24/ET	28	32/ET
DOSING		X		X		X		X	X	X					
CARES	X		X			X					X	X			
PROMIS		X		X			X			X	X				
Fatigue		X		X			X					X			
PROMIS Sex Item		X		X			X								
SF-36v2		X		X			X			X	X				
EQ-5D-5L		X		X			X			X		X			
PGIS	X		X			X						X			

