6.1.1. VARIABLES GENERATED FROM CARES

For each item, weekly scores will be derived as the average of the 7 consecutive daily scores as follows:

Baseline = average of Day -7 to Day -1

Week 5 (Visit 4) = average of Day 22 to Day 28

Week 13 (Visit 7) = average of Day 78 to Day 84

Week 24 (Visit 11) = average of Day 155 to Day 168

For Baseline, Week 5 and Week 13, if more than 3 daily scores out of the 7 days (>50%) within the weekly period are missing, then the score is set to missing.

For Week 24, if more than 7 daily scores out of the 14 days (>50%) within the bi-weekly period

Document : /Users/[REDACTED]/Dropbox (Corvidia Tx)/Corvidia Tx Team Folder/Assets/COR-001/Clinical/RESCUE (COR-001-02)/Manuals & Plans/PRO PAP/Corvidia_RESCUE_PAP_FinalV2.0_24APR2020.docx

Author: [REDACTED] Version No: V2.0

Version Date: 24APR2020

Template No.: [REDACTED] Reference: [REDACTED]

Effective Date: 01Dec2018

Copyright © 2018 [REDACTED] All rights reserved. The contents of this document are confidential and proprietary to [REDACTED] and its subsidiaries. Unauthorized use, disclosure or reproduction is strictly prohibited.

are missing, then the score is set to missing.

Preliminary scoring of the CARES includes the calculation of a Total Symptom Score (TSS). Alternative means of scoring the CARES that are derived from the factor analyses and conceptual considerations may also be defined if supported by the data and if the research team considers these to be plausible and clinically useful alternatives. The following conceptual domains from CARES will be considered: physiological (Short Breath, Swelling, Fatigue, Weakness, Light-headedness, Decreased Appetite, Nausea), psychological (Depression, Concentration, Forgetfulness), pain (Bone / Joints, Nerves, Muscle Cramps), and sensorial (Hand numbness/tingling, Uncomfortable legs, Itching, Dry skin, Dry mouth, Cold) symptoms.

In the preliminary scoring, the daily TSS will be calculated as the average of the 19 daily item scores. A daily TSS score will be calculated if at least 10 out of the 19 items (> 50%) are non-missing. The TSS weekly score will be calculated in the same fashion as the individual items. Higher TSS indicate more symptoms/poorer outcomes.

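### PAP v2.0 section 7.3.5.1 sets the CARES day-pairs one day later than the baseline diary: one of six listed pairs has no scheduled data and one collected pair is left out

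*SAP*

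**What the plan says.** Among its test-retest analyses, PAP v2.0 section 7.3.5.1 plans ICCs between adjacent diary days for CARES, before treatment, in all patients. It describes the data in three ways:

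- In words: "The last 7 days before Day 1 will be considered to define the test and retest time points for CARES collected via eDiary". The section's opening paragraph says the same, referring to the seven days before treatment on Day 1.
- As a window: "two consecutive days from the baseline period (Day -6 to Day 1".
- As a list of pairs: "Days -6 and -5; -5 and -4; -4 and -3; -3 and -2; -2 and -1; -1 and 1".

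Elsewhere the baseline diary period is fixed:

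- Collection, PAP section 2.4.2: "the questionnaire will be answered daily for 7 days prior to dose (Screening Day -7 to Day -1".
- Scoring, PAP section 6.1.1: "Baseline = average of Day -7 to Day -1".
- Baseline definition, PAP section 6.3.1: "i.e., study days -7 through -1".
- PAP section 7.2.1 (completion rate) and the CARES footnote to Table 1 of the clinical SAP give the same seven days.

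Clinical SAP section 3.1.1 states that there is no Day 0. PRO SAP v2.0 section 4.1.1 numbers the day before Day 1 as Day -1.

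**The concern.** The verbal description and the listed pairs cannot both be followed. Day 1 is not one of the days before Day 1, and the list drops Day -7, which the diary covers. Sections 7.2.1 and 7.3.5.1 also use the term baseline period for two different windows.

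This list is an instruction that will be programmed. Someone who follows it has to report an empty or sparse ICC for (-1, 1), use whatever Day 1 entries happen to exist, or substitute a different pair. The plan does not say which.

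The analysis deserves to run as written because it is the only CARES test-retest comparison made wholly before treatment. The other two (patients stable on PGIC or on PGIS) compare baseline with Visit 4, whose diary days, Day 22 to Day 28, come after the first dose. CARES is still under development, and PAP section 7.3.3 intends scores judged sound to be carried into the efficacy evaluation.

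**Working it through.** No sample size, power or alpha is involved. The check is a count of adjacent-day pairs.

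**Inputs**
- Listed window and pairs: Day -6 to Day 1, six pairs (PAP 7.3.5.1).
- Scheduled baseline diary: Day -7 to Day -1 (PAP 2.4.2, 6.1.1, 6.3.1, 7.2.1; clinical SAP Table 1 footnote).
- Day numbering: no Day 0 (clinical SAP 3.1.1).
- Next CARES period: Day 22 to Day 28 (PAP 6.1.1), so no entry is scheduled on Day 1.

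**Formula.** A run of *k* consecutive days gives *k* − 1 adjacent pairs.

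**Step 1: reproduce the plan's list.** With no Day 0, Day -6 to Day 1 is -6, -5, -4, -3, -2, -1, 1. That is 7 days and 7 − 1 = 6 pairs, exactly the six listed. The list therefore agrees with its own window.

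**Step 2: pairs the scheduled diary supports.** Day -7 to Day -1 is also 7 days and 6 pairs.

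**Step 3: compare.**

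| Pair | Listed in 7.3.5.1 | Both days scheduled |
|---|---|---|
| (-7, -6) | no | yes |
| (-6, -5) | yes | yes |
| (-5, -4) | yes | yes |
| (-4, -3) | yes | yes |
| (-3, -2) | yes | yes |
| (-2, -1) | yes | yes |
| (-1, 1) | yes | no |

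Five pairs overlap. One of six listed pairs (1/6 = 17%) has no scheduled data, and one of six collected pairs is not analysed. Each pair yields an ICC for every scale tested, so the shift recurs for each scale.

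**Step 4: Visit -1 window.** The study-flow figure gives Visit -1, nominally Day -7, a window of ±2 days, so it can fall from Day -9 to Day -5. A patient whose diary begins at a visit on Day -6 or Day -5 has no Day -7 entry. If the diary is assumed to run seven days from the actual visit, a Day -6 start would end on Day 1. The documents do not state that rule; they label the period Day -7 to Day -1.

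**The case against.** The best defence is that this is a clerical shift whose intent is plain from the same paragraph. An analyst would notice an empty cell, and PAP section 1 provides for reporting deviations in the final psychometric report. The list could also reflect diaries that started a day late within the Visit -1 window. The first argument bears on severity and stands. The second is an inference, and it conflicts with the seven-day label used elsewhere. Neither reconciles the list with the schedule.

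Several stronger readings are tempting but are not supported:

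- *A sixth ICC would come from a self-selected few.* No document describes who would make a Day 1 entry or why, and the Visit -1 window offers another route.
- *A Day 1 entry is post-treatment.* PAP section 2.3 puts the first dose after all assessments, and CARES looks back 24 hours, so a pre-dose entry would largely describe the day before. The valid criticism is narrower: section 7.3.5.1 does not require a Day 1 entry to be pre-dose, and Day 1 lies outside the defined baseline.
- *The corrected list secures six complete pairs.* It does so only at the nominal schedule. The pair (-7, -6) may have fewer patients because of the Visit -1 window.
- *Reliability evidence or efficacy results are compromised.* Five wholly pre-treatment pairs remain. The plan sets no required number of pairs and no pass mark, only descriptive ICC bands. The standard error of measurement in section 7.3.8.1 uses internal consistency, not test-retest reliability.

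**Conclusion.** The point holds as an internal contradiction in an analysis rule. Section 7.3.5.1 disagrees with its own verbal definition and with the diary schedule. At the nominal schedule, (-1, 1) has no scheduled data and the collected pair (-7, -6) is not analysed.

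The size is one pair of six in an analysis that PAP section 7.1 calls exploratory. Day -7 still contributes to the CARES baseline average, so it is lost only to this analysis. No responder threshold, deterioration endpoint or treatment comparison changes. The correction is worth making because it is free and removes an arbitrary choice; it does not rescue a result.

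The conclusion assumes that the diary ran on the scheduled days. Actual entries may differ for some patients at either end of the week. PAP v1.0 carries the same text, so the revision to v2.0 did not correct it.

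**What to change.** In PAP section 7.3.5.1, change the parenthetical window to Day -7 to Day -1 and list the pairs as (-7, -6), (-6, -5), (-5, -4), (-4, -3), (-3, -2), (-2, -1). This agrees with the section's own verbal definition and with sections 2.4.2, 6.1.1, 6.3.1 and 7.2.1. Showing the number of patients behind each ICC would reveal any thinning at Day -7.

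The cost is one line of text, with no new data and no additional analysis. If the database is already locked, record the change as a deviation in the final psychometric report, as PAP section 1 provides.
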